8.3 Lost to Follow Up

A participant will be considered lost to follow-up if he or she fails to return for 2 scheduled visits and is unable to be contacted by the study site staff.

The following actions must be taken if a participant fails to return to the clinic for a required study visit:

- The site will attempt to contact the participant and reschedule the missed visit and counsel the
 participant on the importance of maintaining the assigned visit schedule and ascertain if the
 participant wishes to and/or should continue in the study.
- Before a participant is deemed lost to follow-up, the investigator or designee will make every
 effort to regain contact with the participant (where possible, 3 telephone calls and, if necessary,
 a certified letter to the participant's last known mailing address or local equivalent methods).
 These contact attempts should be documented in the participant's medical record or study file.
- Should the participant continue to be unreachable, he or she will be considered to have withdrawn from the study with a primary reason of lost to follow-up.

9. Correlative/Special Studies

Not applicable

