7.9 Duration of Therapy and Criteria for Removal from Study

Study Termination Guidelines: A subject's follow-up in the study will end after one of the follow applies:

- Subject's voluntary withdrawal
- Subject lost to follow-up
- Subject death
- Completion of all scheduled study follow-up appointments

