8.2 Participant Discontinuation/Withdrawal from the Study

Participants are free to withdraw from participation in the study at any time upon request.

An investigator may discontinue or withdraw a participant from the study for the following reasons:

- If any clinical adverse event (AE), laboratory abnormality, or other medical condition or situation occurs such that continued participation in the study would not be in the best interest of the participant
- If the participant meets an exclusion criterion (either newly developed or not previously recognized) that precludes further study participation
- Participant lost to follow-up after several attempts to contact subject to schedule study visit.

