12.1 Study Design/Endpoints

Based on the preliminary data and the sample size calculations estimating a difference in mean prepost VAS change between groups of 1 point or greater (on a scale of 1-10), we plan to enroll a total of 110 subjects between the two study sites. Estimated 55 subjects will be enrolled at Weill-Cornell Medical Center/ New York Presbyterian Hospital and 55 subjects will be enrolled at the University of Illinois at Chicago. With 55 patients in the botulinum toxin A injection group and 55 patients in the placebo group (N=110), the study will have more than 90% power to detect a difference in mean in pre-post change between groups of 1.0 point or greater on VAS, using a two-sided t-test and assuming a standard deviation of 1.5 for the mean difference. This calculation allows for 10% attrition rate.

An intent-to-treat design will be followed and all subjects will have scheduled outcome evaluations until the end of the study, death of the subject, or subject refusal. Subjects will be withdrawn from their randomly assigned treatment for considerations of subject safety only. Descriptive statistics including mean, standard deviation, median, range, frequency, and percent will be calculated for the entire cohort as well as by the study arm (botulinum toxin A and unpreserved 0.9% sodium chloride) to assess the results of randomization and identify potential confounders.

The primary analyses of the data will be performed according to subjects' original treatment assignment (i.e., intention-to-treat analyses) and the inclusion of all data from all subjects randomized in the final analysis. To assess the primary endpoint of improvement of pain on a visual analog scale (VAS) between pre-op, 1, 2, and 3 months post-op, a repeated measure of analysis of variance will be performed with one between subject factor (botulinum toxin A versus placebo) and one within subject factor (time). This analysis will also be used for the secondary endpoints: function (MIO/jaw limitation scale) and quality of life (SF12). In the event of significant loss to follow-up, we will explore the use of a linear mixed model to assess the independent effect of the study group on VAS over the study visits. The paired t-test, or the signed-rank test as appropriate, will be used to assess change in pain, function, and QOL between pairs of relevant time points for both study arms.

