To assess the difference in proportion of adverse events between the botulinum toxin A and placebo groups, either the chi-square or Fisher's exact test will be used, as appropriate. All p-values will be two-sided with statistical significance evaluated at the 0.05 alpha level. Ninety-five percent confidence intervals (95% CI) will be calculated to assess the precision of the obtained estimates.

All analyses will be performed in SAS Version 9.4 (SAS Institute Inc., Cary, NC). Note: This section was drafted in conjunction with [name] and [name] in the Division of Biostatistics and Epidemiology, Department of Healthcare Policy and Research. They will be aiding in protocol design and development, data management, study implementation, study monitoring, and data analysis and reporting.

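### The lost-to-follow-up rules can end a participant's follow-up before the 3-month VAS is due, although 12.1 says evaluations stop only at study end, death or refusal

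*Combined protocol and SAP*

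**What the plan says.** All places are in the combined protocol and SAP.

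- **12.1 Study Design/Endpoints**: under an intention-to-treat design, "all subjects will have scheduled outcome evaluations until the end of the study, death of the subject, or subject refusal". The same section commits to analysing all data from everyone randomised.
- **7.9 Duration of Therapy and Criteria for Removal from Study**: the events that end follow-up include "Subject lost to follow-up".
- **8.2 Participant Discontinuation/Withdrawal from the Study**: the third reason for which an investigator may withdraw a participant is "Participant lost to follow-up after several attempts to contact subject to schedule study visit". The other two are an adverse event or other medical condition, and meeting an exclusion criterion.
- **8.3 Lost to Follow Up**: the definition is that "he or she fails to return for 2 scheduled visits and is unable to be contacted by the study site staff". Contact steps begin after one missed visit: an attempt to reschedule, counselling, and where possible three calls and, if necessary, a certified letter. The closing bullet reads "Should the participant continue to be unreachable, he or she will be considered to have withdrawn from the study", with loss to follow-up as the recorded reason.
- **6.1 Schedule of Assessments**: the only post-treatment visits are at months 1, 2 and 3, each with a VAS.

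**The concern.** Being unreachable is not refusal, so loss to follow-up is not among the endings that 12.1 allows. It is nevertheless an ending in 7.9, 8.2 and 8.3. With three visits, a rule that counts two misses can be met while one visit is still to come, and no section says that this visit stays open.

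The study treatment is a single injection given at the start, so 8.1 notes that there is nothing to discontinue. The protocol gives no reason why outcome assessment should close early.

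At stake are month-3 values of the primary endpoint (VAS) and of the secondary endpoints for participants who would have come back. If missing early visits is related to pain or to relief, which the documents do not address, those losses would not be random. Two sites apply the rules, and unclear wording lets them classify the same participant differently.

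**Working it through.** **1. The plan's own power figure.** Section 12.1 states that "the study will have more than 90% power to detect a difference in mean in pre-post change between groups of 1.0 point or greater", "using a two-sided t-test and assuming a standard deviation of 1.5 for the mean difference". The inputs are a difference of 1.0, SD 1.5, 55 per arm and 10% attrition (12.1), 1:1 allocation (6.1.1), and a two-sided alpha of 0.05 (12.1).

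The two-sample t-test has noncentrality δ = 1.0 / (1.5 × √(2/n)) on 2n − 2 degrees of freedom.

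- n = 55: δ = 1.0 / (1.5 × 0.1907) = 3.50; power 93.4%.
- n = 55 × 0.9 = 49.5: δ = 1.0 / (1.5 × 0.2010) = 3.32; power 90.7%.
- Smallest n per arm for 90% power: 49 (90.4%; n = 48 gives 89.8%). Inflated for dropout, 49 / 0.9 = 54.4, which rounds up to 55.

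The stated figure reproduces. The margin is 55 − 49 = 6 per arm (6/55 = 10.9%). The documents give no attrition rate due to early closure. At assumed total attrition of 5%, 15% and 20%, t-test power is 92.2%, 89.1% and 87.1%.

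**2. When the two-visit count is met.** Three visits give eight attended/missed patterns.

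| Visits missed | Second miss falls at | Month 3 still ahead? |
|---|---|---|
| none, 1 only, 2 only, 3 only | never | count not met |
| 1 and 3 | month 3 | no |
| 2 and 3 | month 3 | no |
| 1 and 2 | month 2 | yes; month 3 would have been attended |
| 1, 2 and 3 | month 2 | yes; month 3 would be missed anyway |

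On the two-visit reading, follow-up can close before month 3 only when months 1 and 2 are both missed and contact has failed. A month-3 VAS is actually forfeited only in the fourth row, by someone who would have returned.

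**3. The missing count.** The steps in 8.3 are triggered by one missed visit, and the closing bullet withdraws a participant who stays unreachable without repeating the two-visit condition. The third reason in 8.2 refers to several contact attempts and no number of visits. Read literally, a participant unreachable after missing month 1 could be withdrawn with two visits outstanding.

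**4. The lists of endings side by side.**

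| Section | Events that end follow-up or participation |
|---|---|
| 7.9 | voluntary withdrawal, loss, death, completion of all visits |
| 7.10 | three months after treatment, or death |
| 8.2 | request, medical reason, exclusion criterion, loss |
| 8.3 | loss |
| 12.1 | study end, death, refusal |

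Loss is absent from 12.1. So are the medical and exclusion-criterion withdrawals in 8.2. Those sit less easily with 12.1 than loss does, because such participants can usually still be reached.

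**5. Which analyses would use a recovered month-3 VAS.** The paired comparisons in 12.1 (baseline to month 3) would, and so would the linear mixed model that 12.4.1 holds in reserve for significant loss. A repeated-measures ANOVA run on complete cases, its usual form, would not use a participant lacking months 1 and 2. The plan does not say how that ANOVA treats missing visits.

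**The case against.** The strongest reply is that 8.2 and 8.3 form a single rule. The first sentence of 8.3 defines the term, the bullets set out what must happen before it is applied, and the closing bullet and 8.2 use the term already defined. That reading is tenable. A reader might infer two conflicting thresholds, but no section states a one-visit threshold. What stands is that the count is missing where a site would look for it.

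A reader might also infer that any missed early visit becomes permanent missing data. It does not: 8.3 requires attempts to reschedule and to make contact first, a reachable participant is not lost, and nothing says that data from someone who reappears must be refused. Someone who ignores calls and a letter would often give no month-3 VAS under any rule.

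It is tempting to take the planned 10% attrition, 11 of 110, and count up to 11 × 2 = 22 VAS records lost on the one-visit reading, or 11 on the two-visit reading. Those figures require every expected dropout to follow the early pattern and be closed by this rule. The documents give no such split and no rate of return, so these are extreme upper bounds, not estimates.

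Finally, a participant who misses only month 3 might seem to fit no ending at all under the two-visit rule. Section 7.10 largely answers this by ending follow-up at three months. Such a participant is properly a non-completer under 3.4.

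None of this removes the disagreement between 12.1 and the withdrawal sections, or the early closure when months 1 and 2 are missed.

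**Conclusion.** The concern holds in a limited form. Section 12.1 and sections 7.9, 8.2 and 8.3 give different endings for outcome assessment. The rule in 8.3 can withdraw a participant who misses months 1 and 2, and cannot be contacted, before the 3-month VAS is due. Whether one missed visit is enough is ambiguous.

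The effect is probably small. It falls on participants who go silent early and would have returned, and the documents do not allow that number to be estimated. A reader might take the point as a fault in the sample size, but the stated power is correct on its own inputs (90.7% at 10% attrition). The allowance is nearly used up at that rate, which is a reason to avoid needless loss rather than evidence of an error. Any bias rests on an untested assumption about why visits are missed.

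The change is worth making because it is cheap and serves the plan's own commitment to include all data from all randomised participants.

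**What to change.** 1. In 8.3, use one definition and cross-reference it in 7.9 and 8.2. Suggested wording: *Lost to follow-up is assigned only when the 3-month visit has passed without attendance and the contact attempts listed here have failed. An earlier missed visit is recorded as a missed visit; the remaining visits stay scheduled and are still offered.* Reword the closing bullet of 8.3 and the third reason in 8.2 to match.
2. State when the 3-month visit counts as passed, since the schedule of assessments gives no visit windows.
3. Reconcile the end-of-follow-up lists in 7.9, 8.2, 8.3 and 12.1. Include the 8.2 withdrawals for a medical condition or an exclusion criterion, so that outcome assessment after the single injection continues as 12.1 promises unless the participant refuses. The grounds for those withdrawals are a clinical matter and are not questioned here.
4. State in 12.1 and 12.4 that a later VAS from someone who missed earlier visits enters the mixed model and the paired comparisons.

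The cost is protocol wording and a few extra reminder calls. No visits are added and the sample size does not change.

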9.1 Laboratory Correlative Studies

Not applicable

9.2 Special Studies

Not applicable

10. Measurement of Effect

Efficacy of treatment of myofascial pain disorder with BTA injections will be determined at the completion of the study.

11. Data Reporting / Regulatory Considerations

11.1 Data Collection

The data collection plan for this study is to utilize REDCap to capture all treatment, toxicity, efficacy, and adverse event data for all enrolled subjects.

All subjects enrolled in this clinical trial will have their data entered into the appropriate data entry forms in REDCap by the study staff at Weill Cornell Medicine and the University of Illinois at Chicago.

11.1.1 REDCap

REDCap (Research Electronic Data Capture) is a free data management software system that is fully supported by the Weill-Cornell Medical Center CTSC. It is a tool for the creation of customized, secure data management systems that include Web-based data-entry forms, reporting tools, and a full array of security features including user and group based privileges, authentication using institution LDAP system, with a full audit trail of data manipulation and export procedures. REDCap is maintained on CTSC-owned servers that are backed up nightly and support encrypted (SSL-based) connections. Nationally, the software is developed, enhanced and supported through a multi-institutional consortium led by the Vanderbilt University CTSA.

11.2 Regulatory Considerations

11.2.1 Institutional Review Board/Ethics Committee Approval

As required by local regulations, the Investigator will ensure all legal aspects are covered, and approval of the appropriate regulatory bodies obtained, before study initiation.

Before initiation of the study at each study center, the protocol, the ICF, other written material given to the patients, and any other relevant study documentation will be submitted to the appropriate Ethics Committee. Written approval of the study and all relevant study information must be obtained before the study center can be initiated or the IP is released to the Investigator. Any necessary extensions or renewals of IEC/IRB approval must be obtained for changes to the study, such as amendments to the protocol, the ICF, or other study documentation. The written approval of the IEC/IRB together with the approved ICF must be filed in the study files.

The Investigator will report promptly to the IEC/IRB any new information that may adversely affect the safety of the patients or the conduct of the study. The Investigator will submit written summaries of the study status to the IEC/IRB as required. On completion of the study, the IEC/IRB will be notified that the study has ended.

Neither the Investigator nor BMS will modify or alter this protocol without the agreement of the other. All agreed protocol amendments will be clearly recorded on a protocol amendment form and will be signed and dated by the original protocol approving signatories. All protocol amendments will be submitted to the relevant institutional IEC/IRB for approval before implementation, as required by local regulations. The only exception will be when the amendment is necessary to eliminate an immediate hazard to the trial participants. In this case, the necessary action will be taken first, with the relevant protocol amendment following shortly thereafter.

Once protocol amendments or consent form modifications are implemented at the lead site, Weill Cornell Medicine, updated documents will be provided to participating sites. Weill Cornell Medicine must approve all consent form changes prior to local IRB submission.

Relevant study documentation will be submitted to the regulatory authorities of the participating countries, according to local/national requirements, for review and approval before the beginning of the study. On completion of the study, the regulatory authorities will be notified that the study has ended.

11.2.2 Ethical Conduct of the Study

The Investigators and all parties involved should conduct this study in adherence to the ethical principles based on the Declaration of Helsinki, GCP, ICH guidelines and the applicable national and local laws and regulatory requirements.

This study will be conducted under a protocol reviewed and approved by the applicable ethics committees and investigations will be undertaken by scientifically and medically qualified persons, where the benefits of the study are in proportion to the risks.

11.2.3 Informed Consent

The investigator or qualified designee must obtain documented consent according to ICH-GCP and local regulations, as applicable, from each potential subject or each subject's legally authorized representative prior to participating in the research study. Subjects who agree to participate will sign the approved informed consent form and will be provided a copy of the signed document.

The initial ICF, any subsequent revised written ICF and any written information provided to the subject must approved by IRB prior to use. The ICF will adhere to IRB/IEC requirements, applicable laws and regulations.

11.2.4 Compliance with Trial Registration and Results Posting Requirements

Under the terms of the Food and Drug Administration Modernization Act (FDAMA) and the Food and Drug Administration Amendments Act (FDAAA), the Sponsor-Investigator of the trial is solely responsible for determining whether the trial and its results are subject to the requirements for submission to http://www.clinicaltrials.gov. Information posted will allow subjects to identify

potentially appropriate trials for their disease conditions and pursue participation by calling a central contact number for further information on appropriate trial locations and trial site contact information.

11.2.5 Record Retention

Essential documents are those documents that individually and collectively permit evaluation of the study and quality of the data produced. After completion of the study, all documents and data relating to the study will be kept in an orderly manner by the Investigator in a secure study file, locked in the Principal Investigator's office. Paper and electronic records will be maintained for 2 years after the investigation is discontinued according to FDA guidelines. In addition, all subjects medical records and other source documentation will be kept for the maximum time permitted by the hospital, institution, or medical practice.

12. Statistical Considerations

12.1 Study Design/Endpoints

Based on the preliminary data and the sample size calculations estimating a difference in mean prepost VAS change between groups of 1 point or greater (on a scale of 1-10), we plan to enroll a total of 110 subjects between the two study sites. Estimated 55 subjects will be enrolled at Weill-Cornell Medical Center/ New York Presbyterian Hospital and 55 subjects will be enrolled at the University of Illinois at Chicago. With 55 patients in the botulinum toxin A injection group and 55 patients in the placebo group (N=110), the study will have more than 90% power to detect a difference in mean in pre-post change between groups of 1.0 point or greater on VAS, using a two-sided t-test and assuming a standard deviation of 1.5 for the mean difference. This calculation allows for 10% attrition rate.

An intent-to-treat design will be followed and all subjects will have scheduled outcome evaluations until the end of the study, death of the subject, or subject refusal. Subjects will be withdrawn from their randomly assigned treatment for considerations of subject safety only. Descriptive statistics including mean, standard deviation, median, range, frequency, and percent will be calculated for the entire cohort as well as by the study arm (botulinum toxin A and unpreserved 0.9% sodium chloride) to assess the results of randomization and identify potential confounders.

The primary analyses of the data will be performed according to subjects' original treatment assignment (i.e., intention-to-treat analyses) and the inclusion of all data from all subjects randomized in the final analysis. To assess the primary endpoint of improvement of pain on a visual analog scale (VAS) between pre-op, 1, 2, and 3 months post-op, a repeated measure of analysis of variance will be performed with one between subject factor (botulinum toxin A versus placebo) and one within subject factor (time). This analysis will also be used for the secondary endpoints: function (MIO/jaw limitation scale) and quality of life (SF12). In the event of significant loss to follow-up, we will explore the use of a linear mixed model to assess the independent effect of the study group on VAS over the study visits. The paired t-test, or the signed-rank test as appropriate, will be used to assess change in pain, function, and QOL between pairs of relevant time points for both study arms.

To assess the difference in proportion of adverse events between the botulinum toxin A and placebo groups, either the chi-square or Fisher's exact test will be used, as appropriate. All p-values will be two-sided with statistical significance evaluated at the 0.05 alpha level. Ninety-five percent confidence intervals (95% CI) will be calculated to assess the precision of the obtained estimates.

All analyses will be performed in SAS Version 9.4 (SAS Institute Inc., Cary, NC). Note: This section was drafted in conjunction with [name] and [name] in the Division of Biostatistics and Epidemiology, Department of Healthcare Policy and Research. They will be aiding in protocol design and development, data management, study implementation, study monitoring, and data analysis and reporting.

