6.1.1 Pre-Study Visit

- Informed consent
- Inclusion/exclusion checklist
- Pharmacy order form completed and sent to pharmacy for randomization and processing
 - Eligible subjects will be randomly assigned to Botox injections or placebo treatment groups in a 1:1 ratio using a randomization scheme developed by the [name] and the Division of Biostatistics and Epidemiology, Department of Healthcare Policy & Research

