12.4 Analysis of Endpoints

12.4.1 Analysis of Primary Endpoints

To assess the primary endpoint of improvement of pain on a visual analog scale (VAS) between pre-op, 1, 2, and 3 months post-op, a repeated measure of analysis of variance will be performed with one between subject factor (botulinum toxin A versus placebo) and one within subject factor (time). In the event of significant loss to follow-up, we will explore the use of a linear mixed model to assess the independent effect of the study group on VAS over the study visits.

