12.4.2 Analysis of Secondary Endpoints

The same analysis as that of the primary endpoints will also be used for the secondary endpoints: function (MIO/jaw limitation scale) and quality of life (SF36).

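### The choice of primary VAS model is left open until dropout is known, and the repeated-measures ANOVA named first may not use all the data that the plan promises

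*Combined protocol and SAP*

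**What the plan says.** Section 12.1 declares an intention-to-treat primary analysis and commits to "the inclusion of all data from all subjects randomized in the final analysis". It also plans continued measurement: "all subjects will have scheduled outcome evaluations until the end of the study, death of the subject, or subject refusal".

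For VAS pain at baseline and months 1, 2 and 3, section 12.4.1 says that "a repeated measure of analysis of variance will be performed with one between subject factor (botulinum toxin A versus placebo"; the sentence goes on to add time as the within-subject factor. Section 12.1 says the same.

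Both sections contain a single provision for missing outcomes: "In the event of significant loss to follow-up, we will explore the use of a linear mixed model". No level of loss is named as the trigger. Nothing says whether the mixed model would replace the ANOVA or stand beside it. No missing-data assumption, imputation method or sensitivity analysis is given.

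Related text:
- Section 12.4.2: "The same analysis as that of the primary endpoints will also be used for the secondary endpoints".
- Section 12.1, on software: "All analyses will be performed in SAS Version 9.4". No procedure is named.
- Section 12.1, on sample size: "This calculation allows for 10% attrition rate".
- Section 8.3 defines loss to follow-up for site conduct (two missed visits and no contact). It is not an analysis rule.
- Section 7.11 unblinds the study team once follow-up is complete. Nothing requires the choice of model to be settled before then.

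**The concern.** There are two parts, and they differ in certainty.

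The first is plain from the text. Two models are in play for the primary endpoint, and the switch between them is an undefined judgement made once the amount of dropout is known. A primary analysis should be fixed before that.

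The second depends on how the ANOVA is run. In its ordinary form it needs all four VAS values, so a subject who misses one visit contributes nothing, including the values that were collected. An analysis described as intention-to-treat with all data would then be an analysis of completers. The plan offers the mixed model as a separate remedy for loss, which suggests that its authors had the complete-record form in mind. That is an inference, because SAS 9.4 can also fit a repeated-measures model by likelihood and keep partial records.

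**Working it through.** **Inputs from section 12.1:** 55 per arm (N = 110), difference in mean change 1.0, SD 1.5, two-sided t-test, alpha 0.05, attrition 10%.

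**1. The plan's power figure.** The noncentrality is 1.0 / (1.5 × √(2/n)) on 2n − 2 degrees of freedom.
- n = 55: 1.0 / (1.5 × 0.1907) = 3.50, power 93.4%.
- n = 55 × 0.9 = 49.5: 1.0 / (1.5 × 0.2010) = 3.32, power 90.7%.
- The t-test needs 49 per arm for 90% power (90.4% at 49), and 49 / 0.9 = 54.4, which rounds up to 55.

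The stated figure of more than 90% with 10% attrition therefore reproduces. Power reaches 90.0% at about 48.3 per arm, a loss of 1 − 48.3/55 = 12.2%.

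**2. What complete-record analysis discards at the plan's own attrition.** 0.10 × 110 = 11 subjects. Out of 110 × 4 = 440 scheduled VAS values, the collected values thrown away are:
- last seen at baseline: 11 × 1 = 11 (2.5%)
- last seen at month 1: 11 × 2 = 22 (5.0%)
- last seen at month 2: 11 × 3 = 33 (7.5%)

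A likelihood-based mixed model keeps them all.

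**3. Scattered missed visits (assumed rates, not in the documents).** If each of three follow-up visits is missed independently with probability m, the incomplete share is 1 − (1 − m)³.
- m = 5%: 14.3% incomplete, 55 × 0.857 = 47.2 per arm, power 89.3%.
- m = 10%: 27.1% incomplete, 55 × 0.729 = 40.1 per arm, power 83.8%.

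**4. Can the bias be sized?** The documents give no dropout mechanism and no correlation between visits, so only illustrations are possible. The simulations below assume a true difference of 1.0 at every month, SD of change 1.5, 10% overall dropout after month 1, visit correlation 0.5 or 0.7, and a logistic dropout slope of 1 to 2 per SD (2 in the last two rows).

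| Assumed dropout rule | Complete-record estimate, month 3 | Averaged over months 1–3 |
|---|---|---|
| Same rule in both arms, driven by month-1 level, compound symmetry | 1.00 | 0.98 to 0.99 |
| Same rule, month-1 level, AR(1) | 1.01 to 1.04 | 0.99 to 1.00 |
| Same rule, month-1 change, compound symmetry | 0.92 to 0.97 | 0.90 to 0.96 |
| Same rule, month-1 change, AR(1) | 0.89 to 0.97 | 0.875 to 0.96 |
| Placebo loses 15% (poor month-1 change), botulinum 5% at random, compound symmetry | 0.85 | 0.80 |
| Botulinum loses 10% (poor month-1 change), placebo 10% at random, compound symmetry | 1.11 | 1.14 |

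Across the arm-specific rules, estimates ran from about 0.79 to 1.14. The mixed model returned 1.00 throughout, as it should, because dropout here depends only on observed VAS values. With no true difference and the same rule in both arms, neither method was biased. The sign and size of the bias therefore follow from the assumptions and not from anything in the plan.

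**The case against.** The plan is not silent: the conditional mixed model is a missing-data provision, and the sample size already allows for 10% attrition. At that attrition the harm is small. In simulation with 10% dropout (compound symmetry), complete-record analysis cost about 2 points of power at most on the between-arm contrasts (for month 3, 88.3% to 92.1% against 90.4% to 92.6%). Type I error was nominal for both methods (4.9% against 4.6% to 4.7%) when both arms shared one dropout rule. These are t-type contrasts, not the planned F test. The mixed-model specification proposed below is also only one acceptable choice among several.

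Most of that stands. The provision exists, but it has no trigger and commits only to exploring. The attrition allowance settles how many subjects to enrol, not which records are analysed.

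A reader might go further in four ways that the documents do not support:
- *The trial is underpowered.* The stated power reproduces. It falls below 90% only with more than about 12% incomplete records, which the plan does not predict.
- *The treatment difference will be understated, by some maximum.* Step 4 gives results on both sides of 1.0 and no bound.
- *Partial records will certainly be deleted.* No procedure is named.
- *Some randomised subjects will have no VAS at all.* Table 1 schedules VAS only from the treatment visit, and section 6.1.1 has "Pharmacy order form completed and sent to pharmacy for randomization and processing" at the pre-study visit. But sections 4.2 and 4.3 require a subject-rated VAS of at least 3.5, and section 6.1.1 places the eligibility checklist at the pre-study visit and randomises only eligible subjects. An eligibility VAS before randomisation is therefore implied.

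**Conclusion.** The point holds and should be fixed. It is certain from the text that the primary model is not fixed in advance, because the move to a mixed model rests on an undefined degree of loss and a commitment only to explore. The same gap applies to the secondary endpoints.

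That about 11 of 110 subjects would lose all their collected VAS values is conditional on two things: the complete-record reading of the ANOVA, which is likely but unproven, and attrition at the plan's own 10%. On that reading the analysis conflicts with the promise to include all data.

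The power statement is correct and does not change. Bias in the treatment difference may be nil, an understatement or an overstatement, and no figure for it should be attached to this plan.

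**What to change.** In sections 12.1 and 12.4.1:
- Make the primary analysis a REML linear mixed model on all observed VAS values: baseline and months 1 to 3 as responses, fixed effects for treatment, time and treatment-by-time, unstructured covariance.
- Name one between-arm change contrast before unblinding. The change from baseline averaged over months 1 to 3 fits the endpoint wording; if a single month is meant, name it.
- Delete the conditional sentence on significant loss, and keep the repeated-measures ANOVA as supportive.
- Add one sensitivity analysis that departs from missing at random, computed for the named contrast. An example is multiple imputation that shifts the imputed VAS of botulinum-arm dropouts over a stated range. With 10% dropout, each 1-point shift moves the month-3 difference by 0.10 × 1 = 0.10. It moves the averaged difference by 0.10 × 3/3 = 0.10, 0.10 × 2/3 = 0.07 or 0.10 × 1/3 = 0.03 for subjects last seen at baseline, month 1 or month 2.

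Use the same model in section 12.4.2.

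The cost is a few sentences and one extra analysis in the same software, with no added subjects or visits. The price is reliance on missing at random for the primary result, which the sensitivity analysis is there to test, and a little more model specification.

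A side point: reconcile when the eligibility and baseline VAS are taken relative to randomisation. The schema in section 1.1 puts the checklist and VAS at Day 0 and Table 1 starts VAS at the treatment visit, whereas sections 4.2, 4.3 and 6.1.1 together imply a VAS before randomisation.
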